7.3 Safety Oversight

The RPNI study will have a Data Safety and Monitoring Plan to oversee data security and adherence to study protocols. The study principal investigator, [name] will be ultimately responsible for ensuring proper data procedures and security. In addition, a Data Safety and Monitoring Committee, headed by [name]. [name], Section Chief of Plastic Surgery at the University of Michigan will also oversee the safety of the data processes and convene if necessary.

8. Statistical Considerations

Twenty-five patients will be enrolled into the study (~50% of patients seen in the Multidisciplinary Peripheral Nerve Clinic with post-mastectomy pain in a single year), and of them we expect 23 patients to choose to undergo RPNI surgery (over 90% of the expected enrollment number). Assuming about 10% non-response

or dropout rate, the expected sample size of 20 patients receiving RPNI is expected to give 80% power to detect a mean improvement in post-operative outcome between T1 and T4 (including the primary outcome of pain) of 1.11 standard deviation (SD) or larger using a 0.05 level two-sided test. From our preliminary data based on limb amputations, we expect the pain reduction to be at least 6 points for neuroma pain with an SD of the change of about 1.8 points, which corresponds to a minimum change of 3.3 SD (= 6/1.8). Hence the proposed sample size is expected to give more than adequate power to detect a clinically meaningful level of improvement. For the outcome of opioid use, the proposed sample size is expected to have 83% power using McNemar's test to detect a reduction in opioid use from 78% prior to RPNI to 22% after RPNI at 9 months.

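### Neither power figure in Section 8 (1.11 SD for pain, 83% for opioid use) is reproduced by 20 paired patients at two-sided 0.05 without unstated assumptions; both err on the cautious side

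*Combined protocol and SAP*

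**What the plan says.** Section 8 (Statistical Considerations) plans to enrol 25 patients. It says that "of them we expect 23 patients to choose to undergo RPNI surgery" and, after about 10% non-response or dropout, that "the expected sample size of 20 patients receiving RPNI is expected to give 80% power" for a mean improvement of 1.11 SD or more between T1 and T4, "using a 0.05 level two-sided test". Pain is named there as the primary outcome. The expected pain reduction is at least 6 points with an SD of the change of about 1.8, which the plan expresses as 3.3 SD.

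The claim for the second outcome reads: "For the outcome of opioid use, the proposed sample size is expected to have 83% power using", and the test it goes on to name is McNemar's. The assumed effect is "a reduction in opioid use from 78% prior to RPNI to 22% after RPNI at 9 months". The plan gives no alpha for this test, no version of it (exact, continuity-corrected or uncorrected), no proportions of patients stopping or starting opioids, no within-patient correlation, and no source for 78% and 22%.

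**The concern.** Both claims concern patients compared with themselves, so each should be recoverable from 20 pairs and the stated level. The pain figure needs only n, alpha and power, and 1.11 SD looks far too large for 20 pairs. The opioid figure cannot be recovered from two marginal percentages at all, because McNemar's test uses only the patients whose status changes. A drop of 56 percentage points also looks too large to leave power at only 83%.

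What is at stake is the reliability of the planning figures, not the size of this study. Section 2.3.2 expects the data to support a later multi-institutional trial, whose planners could reuse these numbers. Reduced opioid consumption is also a listed Aim 1 outcome (Section 3.3), so readers need to know what the stated power assumes.

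**Working it through.** **Inputs, all from Section 8.** 23 operated patients less about 10% gives 23 × 0.9 = 20.7, stated as n = 20. Alpha is 0.05 two-sided; it is stated for the mean-improvement test and assumed here for McNemar's test. The opioid margins are 0.78 and 0.22.

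**1. Pain: reproducing 1.11 SD.** For a paired t-test with standardised change d, power = P(|T| > t), where T is non-central t with 19 degrees of freedom and non-centrality d√20, and t = 2.093.

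- At d = 1.11 the non-centrality is 1.11 × 4.472 = 4.96 and power is 99.7%, not 80%.
- Power of 80% is reached at d = 0.660 (non-centrality 2.95). The normal approximation gives (1.960 + 0.842)/4.472 = 0.63.
- In a paired test, 1.11 SD belongs to eight or nine pairs: power is 76.8% at n = 8 and 83.0% at n = 9.
- Suppose 1.11 refers to the SD of the outcome instead of the SD of the change. SD of change = SD × √(2(1 − ρ)), so √(2(1 − ρ)) would have to be 1.11/0.660 = 1.68, giving ρ = 1 − 1.68²/2 = −0.41. A patient's pain at T1 and T4 would have to be clearly negatively correlated.

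**2. Opioid use: reproducing 83%.** Let *stop* and *start* be the shares of all patients who change status in each direction. The margins fix only the difference: stop − start = 0.78 − 0.22 = 0.56, with start anywhere from 0 to 0.22. The number of changers m is binomial(20, stop + start). Given m, the number stopping is binomial(m, stop/(stop + start)). Power is the rejection probability summed over m.

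| Preoperative non-users who start | start | stop | Exact | Continuity-corrected | Uncorrected |
|---|---|---|---|---|---|
| 0% | 0 | 0.560 | 99.5% | 99.5% | over 99.9% |
| 22% (independence) | 0.048 | 0.608 | 91.8% | 91.7% | 95.1% |
| 45% | 0.099 | 0.659 | 83.7% | 82.0% | 89.2% |
| 66% | 0.145 | 0.705 | 78.3% | 74.0% | 84.0% |
| 100% (every patient switches) | 0.220 | 0.780 | 73.4% | 73.4% | 73.4% |

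The exact and continuity-corrected tests dip slightly, to about 70% or 71%, just before the last row.

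Solving for exactly 83% gives these shares of non-users starting: 43% (continuity-corrected), 47% (exact) and 70% (uncorrected).

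**3. What 83% implies.** Take the exact test. Start = 0.22 × 0.473 = 0.104, so the share using at both times is 0.22 − 0.104 = 0.116. Of previous users, 0.116/0.78 = 15% would still use opioids at 9 months, against 47% of previous non-users, about three times as many. The within-patient correlation is (0.116 − 0.78 × 0.22)/(0.78 × 0.22) = −0.32. It is −0.26 for the continuity-corrected test and −0.61 for the uncorrected test.

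**4. Other values of n.** Using 23 or 25 patients raises power further (exact, independence, n = 23: 95.6%). A smaller n can match: the exact test under independence gives 82.4% at n = 16, and an unpaired comparison gives 82.8% with 12 per group. The documents describe neither.

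**The case against.** The strongest reply is that 83% is not refuted. Two margins cannot determine McNemar power, and 83% lies inside the feasible range. The plan also states no alpha for this test: at 0.025 the exact test reaches about 83% if some 30% of non-users start, and at 0.01 if some 10% do. All of this stands. A reader might infer from the table that the figure is impossible, or that exactly 45% of non-users must start; the documents support neither. The defect is an unstated assumption that would have to be an unusual one at the only alpha the plan gives.

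The second reply is that nothing turns on it. Both errors are conservative, the study is a 25-patient pilot, and opioid use is not the primary outcome. This stands too, and it sets the severity.

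A reader might also infer that the study is underpowered for opioid use if baseline use is below 78%. Assuming 50% before and still 22% after, exact power falls to 31% under independence and about 50% with no starters. But the 50% is not in the documents, and holding 22% fixed halves the effect from 56 to 28 points, so lower power is unavoidable. That calculation does not carry the point.

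None of these replies rescues the pain figure, which needs no assumption about switching. The plan itself scales the expected effect by the SD of the change, which supports the paired reading.

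**Conclusion.** The point holds, as a minor one. For pain, 20 pairs at two-sided 0.05 have 80% power at 0.66 SD of the change; the stated 1.11 SD is about 1.7 times that (1.11/0.66). For opioid use, power under ordinary assumptions is about 92% to 95% (independence) or 99.5% (exact test, no starters). The stated 83% needs 43% to 70% of preoperative non-users to start opioids. That pattern is mentioned nowhere in the plan and sits badly with its hypothesis that surgery reduces opioid use (Section 3.1).

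The pain result rests on a paired t-test with the stated n and alpha. The opioid result rests also on carrying 0.05 two-sided over to McNemar's test. Since both figures miss, the paragraph may come from a different n, alpha or design, but the documents do not allow one to say which. Nothing here shows the study to be underpowered: the expected pain effect of 3.3 SD is far above either threshold.

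**What to change.** In Section 8:

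- **Pain.** Restate as 80% power to detect 0.66 SD of the T1-to-T4 change with 20 patients, or state the design, n or alpha that gives 1.11 SD.
- **Opioid use.** State n, alpha, the version of McNemar's test, the assumed proportions stopping and starting, and the source of 78% and 22%. Then replace 83% with the power that these give. As examples at n = 20 and two-sided 0.05, the exact test gives 99.5% with no starters and about 92% under independence. The choice of assumption belongs to the investigators; independence should not be written in by default.
- **Optional.** Add one line showing power for a lower preoperative rate, labelled as an assumption.

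The cost is a few sentences of wording. Sample size, visits and data collection do not change.

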3.3. Study Outcome Measures

Upon successful execution of **Aim 1**, we will demonstrate that:

- 1) RPNI surgery improves patient-reported physical and psychosocial well-being (patient reported depression and anxiety) within three months after surgery.
- 2) Patients who undergo RPNI surgery will report reduced daily opioid consumption within 3 months after surgery.

Upon successful execution of **Aim 2**, we will demonstrate that:

- 1) RPNI surgery provides long-term protection from neuroma recurrence based on physical exam and ultrasound.

4. Study Design

4.1. Methodology: Patients seeking surgical consultation for RPNI surgery in the Multidisciplinary Peripheral Nerve Clinic for chronic post-mastectomy pain will be recruited for this study and followed longitudinally at four time points to evaluate pain, medication usage, anxiety and depression reporting compared to preoperative levels.

Upon enrollment, patients will complete baseline questionnaires including a self-reported medication log (Time 1) and continue their standard non-surgical management plan while awaiting surgery. As an elective surgery, patients' scheduled surgery dates usually occur approximately 3 months after initial consultation. Note: although investigators expect some variability on surgery scheduling, the average time of study involvement for each patient will be 12 months. This represents approximately three months before surgery and nine months after surgery.

Approximately two weeks prior to surgery (during the patient's scheduled preoperative visit), participants will complete the panel of surveys, including medication log (Time 2) and again following RPNI implantation at three (Time 3) and nine months (Time 4) post procedure. The validated PRO instruments will be used to evaluate patients' reported pain experiences, depression, and anxiety (see below). The medication logs will document the details of each patient's medication use over time (see Appendix B Patient Medication log). Study duration will allow patients enrolled during the first 12 months to be followed for the entire study duration.

Presence of neuropathic pain will be confirmed based on detailed history, physical exam findings (e.g. Tinel sign or pins/needles, burning, or shock-like sensations) and local anesthetic nerve blocks which are all part of routine assessment and evaluation at the clinic.

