5.4. Reasons for Withdrawal

A study subject will be discontinued from participation in the study if:

Any clinical adverse event (AE), laboratory abnormality, intercurrent illness, or other medical condition or situation occurs such that continued participation in the study would not be in the best interest of the subject.

Subjects are free to withdraw from participation in the study at any time upon request.

6. Study Schedule

6.1. Study Timeline: The proposed pilot study will run for two years and include three phases: 1) Study initiation; 2) Enrollment and initial data collection; 3) Patient follow-up and final data collection. Investigators plan on beginning in advance of grant funding, so total study time is estimated to be three years. Details of the three phases are provided below.

Phase 1- Study Initiation Month 0-1	Phase 2 – Enrollment and Initial Data Collection Months 1-12	Phase 3 – Patient Follow-up and Final Data Collection Months 13-24
--	--	--

Phase 1: Month 1 involves study training and set-up. Note: Personnel and IRB approval will be in place

prior to Month 1 so Phase 2 (enrollment) will begin as soon as possible.

Phase 2: Months 1-12 of the study will be dedicated to the enrollment and initial follow-up of the RPNI study subjects. All enrollment of subjects will be completed by Month 12 to allow for a complete follow-up period for all patients including an approximate 3 month preoperative and 9 month postoperative period. Additionally, periodic process evaluation and data auditing will occur to assure adherence to study protocol, timeline and sample size goals. Initial data analysis will take place at this time, including descriptive statistics for the study population.

Phase 3: Months 13-24 of the study will involve the conclusion of follow-up data collection for study patients and RPNI surgery for patients enrolled during months 9-12. Data will be reviewed for completeness and cleaned for analysis by the study's biostatistician. Dissemination of study findings will begin during this phase.

Final analyses, report generation, and manuscript submission will take place in the 3-6 months following completion of the funded study during a no-cost extension period.

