Data will be collected longitudinally to assess trends in patient reported outcome (PRO) measures over time (Aim 1). We will assess the distribution of all PRO measures for skewness or outlying values and report summary descriptive statistics at baseline and postop time points for each measure. The extent of non-response at each timepoint will be assessed and reported as a variable of interest. Data will be visualized graphically to see if the reduction in pain occurs gradually or if all pain reduction is complete by a specific time but maintained afterwards. We will model the longitudinally collected follow-up outcomes data using mixed-effects regression models with baseline values of the selected outcome measure and follow-up time as predictors. Using the regression model, we will look for potential predictors of variation in follow-up outcomes. Covariates such as age, race and ethnicity will be examined.

To assess if RPNI surgery results in durable protection from neuroma recurrence (Aim 2), we will monitor physical exam findings at each of the RPNI sites including Tinel sign or evidence of altered sensation in the corresponding dermatome. The initial evaluation at the time of enrollment will provide a baseline of the number of altered sensation categories the patient experiences (shooting pain, burning pain, or tingling). Ultrasound will provide baseline information regarding presence/absence of neuroma, and size of the neuroma. We expect the changes to be in the direction of improvement, but two-sided tests will be used to evaluate 1) presence or absence of any altered sensation physical exam finding, 2) number of altered sensation physical exam findings, 3) presence or absence of ultrasound evidence of neuroma, 4) size of neuroma (if present). As the data will be collected longitudinally at multiple follow-up visits (3 and 9 months postop), we will assess trends in these outcome measures over time.

9. Source Documents and Access to Source Data/Documents

Each participating site will maintain appropriate medical and research records for this trial, in compliance with ICH E6, Section 4.9 and regulatory and institutional requirements for the protection of confidentiality of subjects. Describe who will have access to records.

Source data will originate from medical records of clinical findings (MiChart), observations, and patient completed surveys.

10. Quality Control and Quality Assurance

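### The plan states no T1-to-T4 contrast for the Aim 1 patient-reported outcomes and gives the preoperative visit (T2) no efficacy comparison, so change during the wait for surgery is credited to surgery

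*Combined protocol and SAP*

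**What the plan says.** The power paragraph of Section 8 (Statistical Considerations) expects 20 patients receiving RPNI to give "80% power to detect a mean improvement in post-operative outcome between T1 and T4". It puts the detectable improvement at 1.11 SD, with a two-sided 0.05 test and pain as the primary outcome. It does not name the test.

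For Aim 1, Section 8 then gives one model for the patient-reported outcomes, fitted to "follow-up outcomes data using mixed-effects regression models with baseline values of the selected outcome measure and follow-up time as predictors". The stated use of that model is to look for predictors of variation. Section 6.2 defines baseline as Time 1. The Aim 2 paragraph of Section 8 refers to "multiple follow-up visits (3 and 9 months postop" as the repeated observations. For descriptive statistics, the plan will "report summary descriptive statistics at baseline and postop time points for each measure".

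Section 4.1 has patients "followed longitudinally at four time points to evaluate pain, medication usage, anxiety and depression reporting compared to preoperative levels". Between T1 and T2 they "continue their standard non-surgical management plan while awaiting surgery". T2 falls about two weeks before surgery and collects the full survey panel. Section 3.1 hypothesises a larger reduction than under conservative management. Section 3.3 expects a benefit within three months of surgery.

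**The concern.** The quantity that sizes the trial and the quantity that the written model displays are not the same. Baseline is on the predictor side of the model, there is one treated group, and no contrast is named. An analyst following Section 8 must therefore decide, possibly after seeing the data, how to get a T1-T4 estimate and which test to apply.

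The larger matter is T2. T4-T1 is the sum of T2-T1, the change while waiting on non-surgical care, and T4-T2, the change from just before surgery onward. Reported alone, it attributes both parts to surgery. Patients enrolled when they seek help for pain may well improve before any operation, through regression to the mean or through the care they are already receiving. T2 is the one visit that can show how much of the change preceded surgery, and it bears directly on the comparison in Section 3.1. Section 8 does not say how it will be used.

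**Working it through.** **The plan's own figure.** Section 8 gives 1.11 SD as detectable with n = 20, 80% power and two-sided 0.05. A paired t-test on the T1-T4 change (19 df, noncentrality d√n) gives 80% power at d = 0.66 SD of the change. At d = 1.11 its power is 99.7%. The stated figure is therefore not reproduced by a paired test. It errs on the cautious side, and nothing below depends on it.

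**What the written model contains.** Take complete data, T3 and T4 as responses at 3 and 9 months, and a random intercept:

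score = α + β × (T1 score) + γ × time + patient effect + error

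- Time term: 6γ = mean T4 − mean T3. If a benefit is complete by three months and held, this is zero.
- T1-T4 change: (α + β × mean T1 + 9γ) − mean T1 = mean T4 − mean T1. In fitted examples with complete data, this equalled the paired mean difference to under 1e-14.

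So the powered quantity can be obtained, but only as a derived contrast that the plan does not state.

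**What T4-T1 does with change before surgery.** These are assumptions, as the plan gives none of them: n = 20, visit SD 1, equal correlation r between visits, complete data, paired t-tests at two-sided 0.05. The scenario is a 1 SD fall between T1 and T2 and no change afterwards.

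- SD of a difference between two visits = √(2(1 − r)). At r = 0.5 this is 1.
- T4-T1: d = 1/1 = 1, noncentrality √20 = 4.47, rejection 98.9%. A simulation gave the same figure.
- T4-T2: the true difference is 0, so rejection is 5% by construction (4.9% in simulation).
- Range for T4-T1: at r = 0.3, d = 1/1.183 = 0.845 and rejection is 94.8%. At r = 0.7, d = 1/0.775 = 1.29 and rejection is above 99.9%.

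**Whether a single difference-of-changes contrast would settle it.** (T3-T2) − (T2-T1) has variance (1 + 4 + 1)(1 − r) = 6(1 − r), so its SD is 1.73 at r = 0.5.

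| True change (r = 0.5) | Mean of contrast | d | Result |
|---|---|---|---|
| No preoperative change, 1.5 SD surgical drop | −1.5 | 0.87 | 95.6% power |
| 0.5 SD preoperative fall, 1 SD surgical drop | −0.5 | 0.29 | 23% power |
| 1 SD preoperative fall, no surgical effect | +1 | 0.58 | significant against surgery in 69% |

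The contrast is fragile: preoperative improvement removes its power and can turn it against surgery. It is not suitable as the main evidence.

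**The case against.** Much can be said for the plan.

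- A reader might infer that the model cannot estimate the T1-T4 improvement. It can, as the algebra shows. What is missing is a statement of the contrast and its test.
- A reader might infer that the time coefficient is the Aim 1 test, so that a held benefit would be reported as a null result. Section 8 never says so. It uses the model to look for predictors, and T4 versus T3 is a fair answer to its question whether pain reduction is maintained.
- A reader might take follow-up to include T2, because Section 6.1 speaks of a "complete follow-up period for all patients including an approximate 3 month preoperative and 9 month postoperative period". That sentence concerns study duration. The analysis text itself ties follow-up visits to 3 and 9 months, so no figures are offered for the wider reading.
- T2 is not wholly unused. Non-response is reported at each timepoint, and the planned graphs may show T2.
- Patients who decline surgery may stay in the study, about 2 of 25 (25 − 23). This matters little here, since T3 and T4 are timed from surgery and the power statement concerns patients receiving RPNI.
- Opioid use is outside this point, because Section 8 names McNemar's test for it.

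These objections narrow the point but do not remove it. No sentence names the T1-T4 analysis of patient-reported outcomes, and none gives T2 a role in judging efficacy.

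**Conclusion.** The point holds as a gap in specification with a real consequence for interpretation. No term or stated contrast of the only Aim 1 patient-reported outcome model is the T1-T4 improvement on which the trial is powered. T2 is fully collected but has no efficacy contrast and is left out of the named descriptives, although it closes the only scheduled interval on non-surgical care alone.

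On its own, T4-T1 counts preoperative change as a surgical effect. A 1 SD fall wholly before surgery makes it significant in about 99% of trials (95% to over 99.9% for correlations of 0.3 to 0.7), against about 5% for T4-T2. These rates rest on the assumed visit SD, correlation and trajectory, and do not predict that such a fall will occur. That T4-T1 is the sum of the two intervals depends on none of these assumptions.

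The documents do not support the stronger conclusion that the model is wrong or that the planned test would miss a true benefit. This is a cheap improvement.

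**What to change.** Change the wording of Section 8:

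1. In patients who receive RPNI, fit a mixed model with T1, T2, T3 and T4 all as responses and visit as a four-level factor, with unstructured within-patient covariance and Kenward-Roger degrees of freedom.
2. Name T4-T1, two-sided 0.05, as the primary contrast, matching the power statement. Name T3-T1 as secondary, matching the expectation in Section 3.3 of benefit "patient reported depression and anxiety) within three months after surgery".
3. Add T2 to the descriptive statistics. Report T2-T1 (change on conservative care) and T3-T2 and T4-T2 (change after surgery) with confidence intervals, as secondary.
4. If (T3-T2) − (T2-T1) is reported, label it exploratory. State that regression to the mean before surgery can bias it against surgery and that its power falls sharply with any preoperative improvement.
5. Keep the baseline-adjusted model, with follow-up defined as T3 and T4, for predictors and for maintenance from 3 to 9 months.
6. State that single-group contrasts do not exclude regression to the mean or time effects.

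The cost is a few more secondary contrasts to report. No visits, patients or data are added. With complete data the model's T4-T1 estimate equals the paired mean difference, so the point estimate is unchanged from that of a paired test.

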The central hypothesis for this study is that intercostal RPNI surgery significantly reduces chronic post-mastectomy pain with absence of painful neuroma recurrence.

Aim 1: To examine the use of RPNI surgery to reduce post-mastectomy pain and opioid consumption.

We will obtain patient-reported outcomes (PRO's), using previously validated tools, to examine the effect of RPNI surgery on post-mastectomy pain and opioid use. Patients who are at least six months removed from mastectomy and exhibit clinical signs and symptoms of neuropathic pain will be asked to enroll in this IRB-approved study. Patients will be excluded if mastectomy occurred less than six months prior or if they have had previous surgical interventions to treat pain. Upon completion of Aim 1, we will assess the association between intercostal RPNI surgery and neuropathic pain in post-mastectomy patients.

Aim 2: To demonstrate absence of neuroma recurrence in post-mastectomy patients after intercostal RPNI surgery.

Neuroma recurrence in patients treated with intercostal RPNI will be evaluated using physical exam findings and ultrasound (14, 17-20). Patients will be assessed immediately following enrollment, preoperatively, and at subsequent intervals (3 and 9 months) following RPNI. Upon completion of Aim 2, we will demonstrate that intercostal RPNI surgery provides durable relief from neuroma recurrence.

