2.4.2. Known Potential Benefits

The prescribing of opioid medications to treat pain, including chronic pain following surgery, has become a critical issue across the U.S. Reports indicate that 10% of opioid naïve patients who undergo mastectomy require opioids for pain relief at least three months after surgery and up to 40% of patients who undergo mastectomy report post-surgical pain lasting greater than three months. Three years after surgery, nearly 25% of patients continue to report moderate persistent pain after the mastectomy procedure which involves the transection of small sensory nerves present and traveling through excised breast tissues. This study is a novel approach to improving post-mastectomy quality of life and reducing dependence on pain medications and the ensuing risk of dependence and addiction.

3. Hypotheses and Objectives

Aim 1: To examine the use of RPNI surgery to reduce post-mastectomy pain and opioid consumption.

3.1. Hypothesis: Neuroma resection and RPNI surgery to treat intercostal neuromas will reduce patient-reported post-mastectomy pain, depression/anxiety scores, and opioid use to a greater degree than will conservative neuropathic pain management.

3.1.2. Objective: Identify patients with post-mastectomy pain who have been referred to the Multi-Disciplinary Peripheral Nerve (MDPN) or Plastic Surgery Clinics and evaluate their neuropathic pain, depression and anxiety levels, and opioid use pre- and post-treatment.

We will enroll patients seeking surgical treatment for chronic post-mastectomy pain upon referral to our institutional Multi-Disciplinary Peripheral Nerve Pain (MDPN) Clinic or Plastic Surgery. The presence of neuropathic pain will be evaluated by the combined efforts of plastic surgeons, peripheral nerve surgeons, anesthesia pain providers, and physiatrists. Each patient's medication usage will be logged at pre- and post-surgical timepoints.

Aim 2: To demonstrate absence of neuroma recurrence in post-mastectomy patients after intercostal RPNI surgery.

3.2. Hypothesis: Intercostal nerves treated with RPNI will remain free of neuroma recurrence through nine months after RPNI surgery.

3.2.2. Objectives: Evaluate patient reported outcomes of intercostal RPNI surgery and clinical indicators such as routine ultrasound review and physical exam.

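### Aim 2 claims freedom from neuroma recurrence, but section 8 tests change from enrolment and plans no post-operative proportion or interval

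*Combined protocol and SAP*

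**What the plan says.** **The claim.** Aim 2 is worded "To demonstrate absence of neuroma recurrence in post-mastectomy patients after intercostal RPNI surgery" (section 2.3, repeated in section 3). Its hypothesis in section 3.2 is "Intercostal nerves treated with RPNI will remain free of neuroma recurrence through nine months after RPNI surgery". Section 3.3 expects the study to show long-term protection. The indicators are named: "Neuroma recurrence in patients treated with intercostal RPNI will be evaluated using physical exam findings and ultrasound" (section 2.3). Sections 4.2.4 and 4.2.5 list the exam signs and the ultrasound appearance.

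**The analysis.** Section 8 states for Aim 2 that "we will monitor physical exam findings at each of the RPNI sites including Tinel sign or evidence of altered sensation in the corresponding dermatome". It then sets the reference point: "The initial evaluation at the time of enrollment will provide a baseline of the number of altered sensation categories the patient experiences". Ultrasound at baseline supplies presence and size of neuroma. The text continues "We expect the changes to be in the direction of improvement", says that "two-sided tests will be used to evaluate 1) presence or absence of any altered sensation physical exam finding", and adds the number of exam findings, ultrasound evidence of neuroma, and neuroma size. Because there are visits at 3 and 9 months, "we will assess trends in these outcome measures over time".

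For Aim 2, section 8 gives no post-operative proportion, confidence interval, reference rate or threshold, and no rule that turns exam and ultrasound findings into a recurrence. The descriptive summaries it promises before and after surgery are for the patient-reported measures of Aim 1.

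**The concern.** The aim describes a state after surgery: treated nerves without recurrence. The planned tests describe a difference from before surgery. These are different questions, and the design separates them further. Section 5.1.2 excludes patients whose exam does not suggest neuropathic pain, so nearly every patient should have a finding at enrolment. Section 4.2.6 has the symptomatic neuroma excised. Some change from enrolment is therefore expected even if a good share of patients still have findings, or have them again, at nine months.

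The unit is also unclear. The baseline counts categories of altered sensation per patient, while follow-up is at each RPNI site, and the Fig 8 caption shows that one patient can have several treated nerves.

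Aim 2 is one of two aims of a pilot that section 2.3 says should supply preliminary data for a multi-institutional trial. What that trial needs is an estimate of durability with its uncertainty. The stated analysis does not produce one.

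**Working it through.** The plan gives no rate, precision or power for Aim 2, so there is no figure of its own to reproduce. The power statements in section 8 concern pain and opioid use.

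**Inputs from section 8:** 25 enrolled, 23 expected to have surgery, 20 expected to be evaluable.
**Assumptions:** an exact McNemar test (none is named); all 20 positive on exam at enrolment (suggested by section 5.1.2, not guaranteed); two treated nerves per patient for the per-nerve figures (no count is given).

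**Formulas.** Exact McNemar with b changes one way and none the other: p = 2 × 0.5^b. Intervals are exact (Clopper-Pearson) 95%. For 0 of n, the upper limit is 1 − 0.025^(1/n).

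1. **Change from enrolment.**
   - b = 5: p = 2 × 0.5^5 = 0.0625.
   - b = 6: p = 2 × 0.5^6 = 0.031.
   - The test is therefore significant with 20 − 6 = 14 of 20 patients still positive (70%, 95% CI 45.7% to 88.1%).

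2. **Trend from 3 to 9 months.** If 5 of 20 patients go from clear to positive and none clears, p = 0.0625. A finding of no significant worsening is thus compatible with findings returning in 25% of patients (95% CI 8.7% to 49.1%).

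3. **The best possible result, per patient.**
   - 0 of 20: upper limit 1 − 0.025^(1/20) = 16.8%.
   - 0 of 23: 14.8%. 0 of 18: 18.5%.

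4. **Per nerve, two nerves per patient.** Effective number = 40 / (1 + ICC), where ICC is the within-patient correlation.
   - ICC 0: 40 nerves, upper limit 8.8%.
   - ICC 0.5: 40 / 1.5 = 26.67, upper limit 12.9%.
   - ICC 1: 20, upper limit 16.8%.

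5. **Missing assessments.**
   - If all 20 assessed patients are free and the other 23 − 20 = 3 count as not free, 20/23 = 87.0% are free (95% CI 66.4% to 97.2%).
   - Section 6.2 takes ultrasound from routine care. If only 15 or 10 patients have a 9-month scan and none is positive, the upper limit is 21.8% or 30.8%.

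**The case against.** **This is a small pilot with pain as its primary outcome.** True, and it limits the weight of the point. It does not make a test of change answer Aim 2.

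**No test is named, so change from enrolment is an inference.** That stands as a caveat. The words baseline and changes, and the lack of any reference rate for a one-sample test, leave no other workable reading.

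**Presence or absence is recorded at follow-up, so a proportion can be derived.** Correct, and this is why the repair is cheap. But it is not planned. Without a stated definition, unit and rule for missing scans, several versions could be computed and one chosen after the data are seen.

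**The trends cover durability.** They bear on it, but no interval is planned for them, and step 2 shows that a non-significant trend is weak evidence. For ultrasound a 3-to-9-month trend may not be possible: the section 6.2 table schedules it only at Times 1 and 4, although the section 6.2 text for Time 3 lists ultrasound results.

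**The 14 patients in step 1 may never have cleared.** This stands. A reader might infer a 70% recurrence rate from the example. The documents do not support that, because persistent findings are not returned ones. The example shows only that significance does not imply freedom from findings.

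**What counts as recurrence is a clinical definition.** This also stands. The central hypothesis in section 2.3 speaks of painful recurrence and section 3.2 does not. A reader might infer that any single exam sign or any ultrasound mass should count. The documents do not settle this.

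**Conclusion.** The concern holds. Followed as written, the Aim 2 analysis can show improvement from enrolment but cannot support the statement that treated nerves stay free of recurrence. The size is illustrated by p = 0.031 with 14 of 20 patients still positive, under an exact McNemar test and universal baseline positivity. Separately, demonstrating absence is out of reach at this sample size: per patient, even 0 of 20 leaves an upper limit of 16.8%. A per-nerve limit could be lower, depending on the number of nerves and the within-patient correlation.

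Two stronger readings are not supported. A reader might infer that the plan has no recurrence indicators, but it names them and follows them at each treated site. A reader might also infer that the investigators would report a significant test as absence of recurrence; the text leaves that open but does not say it. The point does not touch the pain analysis. It should be fixed before the data are analysed.

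**What to change.** **Main Aim 2 result.** Report the proportion of operated patients free of recurrence through nine months, meaning at both the 3- and 9-month assessments, with an exact 95% confidence interval. Status at nine months alone would miss findings present at three. Add a per-nerve version that allows for clustering within patient.

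**Definition.** Before analysis, the investigators should define recurrence from the indicators already in sections 4.2.4, 4.2.5 and 8, and reconcile the painful recurrence of section 2.3 with the unqualified wording of section 3.2. They should state how an additional RPNI operation, already recorded under section 4.2.7, counts in the main result.

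**Reporting.**
- Give exam and ultrasound proportions separately, each with the number assessed.
- Add a sensitivity analysis that counts operated patients without a 9-month assessment as not free.
- Describe persistent, returned and transient findings separately.
- Reconcile the ultrasound timing between the section 6.2 table (Times 1 and 4), the section 6.2 text for Time 3, and the 3- and 9-month trends of section 8.
- Keep the four baseline comparisons and the trends as supportive evidence of improvement.
- In the aim and outcome statements, replace the promise to demonstrate absence with the estimate and its confidence limit.

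**Cost.** Mostly wording and a little more analysis, with no change to sample size or treatment. The treated site must be recorded with each follow-up finding. Some patients may lack a scan, because ultrasound comes from routine care. The Aim 2 claim becomes more modest.
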